5. TREATMENT PLAN

5.1 Study Design and Duration

This study is an open-label, single center trial assessing the safety and feasibility of using perioperative neoadjuvant and adjuvant immune-therapy for resectable liver or lung metastases.

Cohort A will consist of neoadjuvant tremelimumab 75 mg IV flat dose and durvalumab 1500 mg IV flat dose. Adjuvant therapy will consist of 4 monthly doses of durvalumab 1500mg IV.

Cohort B will consist of neoadjuvant oleclumab 3000 mg IV flat dose followed by durvalumab 1500 mg IV flat dose. Adjuvant therapy will consist of 4 months of oleclumab every two weeks at 3000 mg IV flat dose and durvalumab every 4 weeks at 1500 mg IV flat dose. On days oleclumab and durvalumab are both administered, oleclumab will be given first (see Section 8.1.4).

Cohort C will consist of neoadjuvant durvalumab 1500 mg IV flat dose then Monalizumab 750mg IV flat dose. Adjuvant therapy will consist of 4 months of durvalumab 1500 mg IV flat dose and monolizumab 750 mg, both administered every four weeks.

[figure not shown]
Cohort A has been enrolling since the study initiation and will enroll up to 25 patients. At the time of amendment activation initially opening, cohort B may enroll 5 patients followed by 5 patient enrollment for cohort C. Enrollment will continue in this alternating manner with approximately 5 patient blocks at a time for these cohorts. Enrollment may be adjusted based on Medimmune/MD Anderson determined priorities and drug availability. Cohort B and C will each be 15 patients.

[figure not shown]

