7.4 Recording of Adverse Events

Adverse events will be recorded on the eCRF (Protocol Data Management System/Clinical Oncology Research System - PDMS/CORe) using a recognized medical term or diagnosis that accurately reflects the event. Adverse events will be assessed by the investigator for severity, relationship to the investigational product, possible etiologies, and whether the event meets criteria of an SAE and therefore requires immediate notification to MedImmune Patient Safety. See Section 7.2 for the definition of SAEs. If an AE evolves into a condition that meets the regulatory definition of “serious,” it will be reported on the SAE Report Form. Infusion of biological products is commonly associated with infusion-related reactions.

Anaphylaxis and infusion-related reactions have some common manifestations and may be difficult to distinguish from each other. Infusion-related reactions are commonly observed during or shortly after the first time exposure to therapeutic mAbs delivered through intravenous infusion. These reactions are less common following subsequent exposures. Unlike infusion-related reactions, anaphylaxis is a rare event, usually occurring after subsequent exposure to an antigen, and it is most commonly accompanied by severe systemic skin and/or mucosal reactions. The investigator is advised to carefully examine symptoms of adverse reactions observed during or shortly after exposure to Durvalumab and tremelimumab, and consider the above mentioned facts prior to making a final diagnosis.

Reactions occurring at the time of or shortly after subsequent infusions of investigational product are to be judged by the investigator at his/her own discretion. For the Investigator's convenience and in order to facilitate consistency in judgments, a copy of the National

Institute of Allergy and Infectious Diseases (NIAID) and Food Allergy and Anaphylaxis Network (FAAN) guidance for anaphylaxis diagnosis is provided in Appendix 3.

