8.1.4 Treatment Administration

The first day of dosing is considered Day 1.

For cohort A tremelimumab will be administered first; the durvalumab infusion will start approximately 1 hour (maximum 2 hours) after the end of the tremelimumab infusion. Standard infusion time for each is approximately 60 minutes In the event that there are interruptions during infusion, the total allowed time should not exceed 8 hours at room temperature.

For cohort B, oleclumab will be infused with standard infusion time of approximately 60 minutes. The drug will be administered at room temperature (approximately 20 to 25°C) by controlled infusion into a peripheral or central vein. Standard infusion time for Oleclumab (MEDI9447) is 1 hour; however, if there are interruptions during infusion, the total allowed time should not exceed 4 hours at room temperature. If this duration is met, then the remainder of the dose should be abandoned and should not be completed with a second prepared dose. On days where both oleclumab and durvalumab are administered, durvalumab infusion will start no less than 15 minutes after the end of Oleclumab infusion. Standard infusion time for durvalumab is 1 hour; however, if there are interruptions during the infusion, the total allowed time should not exceed 8 hours at room temperature.

Do not co-administer other drugs through the same infusion line.

Flush the IV line with a volume of IV diluent equal to the priming volume of the infusion set used after the contents of the IV bag are fully administered, or complete the infusion according to institutional policy to ensure the full dose is administered and document if the line was not flushed.

For cohort C durvalumab will be infused first with standard infusion time of approximately 60 minutes. In the event that there are interruptions during infusion, the total allowed time should not exceed 8 hours at room temperature.

Each dose of intravenous investigational product should be administered using the following guidelines:

1. Investigational product(s) must be administered at room temperature by controlled infusion into a peripheral vein or central line. Prior to the start of the infusion, ensure that the bag contents are at room temperature to avoid an infusion reaction due to the administration of the solution at low temperatures.

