8.1.5 Monitoring of Dose Administration

Subjects will be monitored prior to, during, and after infusion of Durvalumab, Tremelimumab, Oleclumab and Monalizumab.

Refer to Table 10.4 for monitoring schedule for vitals during dose administration for all cohorts.

In the event of Grade \leq 2 infusion-related reaction, the infusion rate of Durvalumab, Tremelimumab, Oleclumab or monalizumab may be decreased by 50% or interrupted until resolution of the event (up to 4 hours) and re-initiated at 50% of the initial rate until completion of the infusion. In subjects experiencing Grade \leq 2 infusion-related reaction, subsequent infusions may be administered at 50% of the initial rate.

Primary prophylaxis against infusion-related reactions is not permitted during this study in order to avoid obscuring a potential safety signal and enable a future assessment regarding whether premedications should be required for all subjects in future studies. However, at the discretion of the investigator, secondary prophylaxis (ie, prevention of infusion-related reaction following initial episode) is appropriate and will be permitted. Acetaminophen and/or an antihistamine (eg, diphenhydramine) or equivalent medications per institutional standard may be administered at the discretion of the investigator. If the infusion-related reaction is Grade 3 or higher in severity, treatment with Durvalumab, tremelimumab, Oleclumab and monalizumab will be discontinued.

As with any mAb, allergic reactions to dose administration are possible. Therefore, appropriate drugs and medical equipment to treat acute anaphylactic reactions must be immediately available, and study personnel must be trained to recognize and treat anaphylaxis.

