13.3 Interim Monitoring

A Bayesian sequential monitoring design[66, 67] will be used to monitor the trial for surgery and toxicity rates. Generally, interim analyses will begin after 3 patients become evaluable, and will then be performed continuously to ensure that patients are exhibiting reasonable toxicity and surgery rates to continue the trial. Specific rules are in each subsection below. Since 1-2 patients are expected to be enrolled each month, monitoring data will be kept up-to-date and the tables below checked prior to consenting each patient once the 3rd patient in each cohort has been on study 4 weeks after the first dose of Durvalumab. Enrollment will not need to wait for the previous patient to become evaluable, but the rules will be checked for all evaluable patients before consenting each patient. This includes a risk of 1-2 patients entering on the study beyond the designed stopping rules, which is considered a reasonable risk. If accrual occurs faster than 1-2 patients per month, this practice will be reconsidered. All calculations for stopping boundaries and operating characteristics were performed in Multicenter Lean Desktop v2.1.

Patients will be evaluable once they have received the first dose of Durvalumab/tremelimumab, durvalumab/oleclumab or durvalumab/monalizumab and have then had 8 weeks time to go to surgery. If surgery has not occurred by 8 weeks then for monitoring these patients will have been considered not to have gone to surgery even if they do after 8 weeks. Patients will be allowed up to 12 weeks to complete surgical resection. If surgical resection is not done within 12 weeks from then patient will be removed from clinical trial

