13.3.2 Interim Analyses for Toxicity

Under the same model described for futility, toxicities will be monitored assuming a prior probability of toxicity following $\text{Beta}(0.6, 1.4)$ in the current treatment arm against a constant rate of 0.30. Based on a previous study, we assume that a 15% rate of toxicity events would be acceptable and a 30% rate of toxicity would be unacceptable. [68] For trial monitoring and decisions about future trials, extreme toxicities (TOX) will be defined as any grade 3 or higher adverse event that is possibly, probably, or definitely related to any therapy received on this protocol and occur between the first dose of Durvalumab and surgery (or 4 weeks after that dose if the patient does not receive surgery as scheduled) with the following exception. Any grade 3 adverse event that is

potentially treatable with steroids will only count as an extreme toxicity if it does not improve to grade 2 or better within 2 weeks. Grade 3 nausea or vomiting that responds to anti-emetics within 72 hours and asymptomatic grade 3 or 4 lipase or amylase elevations will not count as TOX. The trial will be terminated if $\text{Prob}(\Theta_{\text{TOX}} > 0.30 | \text{data}) > 0.9$, where Θ_{TOX} is the proportion of patients experiencing a TOX event. Following this rule, the trial will be terminated according to the following table once the first 3 patients are evaluable.

If there are this many patients (or more) with TOX	3	4	5	6	7	8	9	10	11
Stop the cohort if there are this many (or fewer) patients who are evaluable (have TOX or completed 4 weeks after first Durvalumab dose without TOX)	3	7	9	12	14	17*	20	22	25*

* Always stop with 25 patients in Cohort A, but if 11 or more patients have TOX, then this treatment regimen is too toxic for further use. Always stop at 15 patients in Cohorts B and C, but if 8 or more patients have TOX, then this regimen is too toxic for further use.

Three patients in each cohort will be accrued first. If 3 of the 3 patients have TOX, stop that cohort and the treatment will be declared as too toxic for that cohort. If there is at least 1 patient with surgery without TOX, the next patient will be entered in the study, unless the trial needs to stop according to futility boundaries above. Check continuously as described above for toxicity assuming the trial does not stop for futility first. The operating characteristics for the combined futility and toxicity are summarized in the following table

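### The TOX window in 13.3.2 opens at the first durvalumab dose, so a severe reaction to the tremelimumab given before it in Cohort A escapes the toxicity stopping rule

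*Combined protocol and SAP*

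**What the plan says.** **TOX window.** 13.3.2 counts grade 3 or higher events related to any protocol therapy, but only those that "occur between the first dose of Durvalumab and surgery" (or within 4 weeks of that dose if surgery does not take place as scheduled). Grade 3 events potentially treatable with steroids count only if they fail to improve within 2 weeks.

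**Evaluability.** The boundary table in 13.3.2 counts patients who have TOX or have "completed 4 weeks after first Durvalumab dose without TOX". 13.3 starts the checks "once the 3rd patient in each cohort has been on study 4 weeks after the first dose of Durvalumab". For surgery, 13.3 says "Patients will be evaluable once they have received the first dose of Durvalumab/tremelimumab", or the corresponding pair in the other cohorts, and have then had 8 weeks to reach surgery.

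**Infusion order.** 8.1.4 reads: "For cohort A tremelimumab will be administered first; the durvalumab infusion will start approximately 1 hour (maximum 2 hours") after the tremelimumab infusion ends. 5.1.2.1 also puts tremelimumab first. For Cohort B, 5.1 states "On days oleclumab and durvalumab are both administered, oleclumab will be given first" and 8.1.4 agrees, but 5.1.2.2 says durvalumab always comes first. For Cohort C, 5.1 and 8.1.4 put durvalumab first, while 5.1.2.3 gives both orders.

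**Consequence of a severe reaction.** 8.1.5: "If the infusion-related reaction is Grade 3 or higher in severity, treatment with Durvalumab, tremelimumab, Oleclumab and monalizumab will be discontinued".

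**The concern.** The rule sets out to count toxicity from any drug in the regimen, yet its clock starts with one particular drug that is not the first given in Cohort A. A patient who has a grade 4 reaction to tremelimumab is discontinued under 8.1.5 before durvalumab. That event precedes the window, so it is not TOX, and there is no durvalumab dose from which to complete 4 weeks. The patient is in neither the numerator nor the denominator of the toxicity rule.

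The gap falls at a relevant time. 7.4 says "Infusion-related reactions are commonly observed during or shortly after the first time exposure to therapeutic mAbs", and the neoadjuvant infusion is normally the patient's first exposure. The same TOX count also supports the verdict on whether a regimen is too toxic for further use, so the definition matters beyond the interim looks.

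**Working it through.** **1. Length of the gap.** Under 8.1.4 tremelimumab runs about 1 hour and durvalumab starts about 1 hour (at most 2) after it ends: 1 + 1 = 2 hours to 1 + 2 = 3 hours. 5.1.2.1 has durvalumab follow immediately, which would leave about 1 hour. Where oleclumab is first in Cohort B, 8.1.4 gives 60 + 15 = 75 minutes or more.

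**2. Reproducing the plan's figures.** Inputs from 13.3.1 and 13.3.2: stop for toxicity if Pr(θ > 0.30) > 0.90 under Beta(0.6 + x, 1.4 + n − x), with x TOX in n evaluable patients. Stop for futility if Pr(θ < 0.60) > 0.90 under Beta(1.2 + s, 0.8 + n − s), with s surgeries. Exact enumeration, toxicity and surgery independent as the plan assumes, a look after every patient from the third, and the look at full size not counted as early stopping. At surgery rate 0.80:

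| True toxicity | N | Pr(stop early), plan | Recomputed | Mean N, plan | Recomputed |
|---|---|---|---|---|---|
| 0.30 | 25 | 0.27 | 0.266 | 20.6 | 20.6 |
| 0.30 | 15 | 0.22 | 0.223 | 13.1 | 13.1 |
| 0.40 | 25 | 0.59 | 0.585 | 15.8 | 15.8 |
| 0.40 | 15 | 0.47 | 0.470 | 11.1 | 11.1 |

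The nine printed toxicity boundaries all satisfy the 0.90 criterion. (Three TOX also satisfies it at 4 patients, 0.935, where the table lists 3. This does not affect what follows.)

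**3. One missed event.** Take 7 treated patients with 4 qualifying events, one of them before durvalumab.

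- All counted: 4 in 7, Pr(θ > 0.30) = 0.901, so stop.
- Durvalumab never given, patient not evaluable: 3 in 6, 0.800, so continue.
- Patient kept as a non-event (for example, durvalumab given later): 3 in 7, 0.717, so continue.

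In the extreme case where the first three patients all react before durvalumab, counting them gives 3 in 3 (0.976, stop), while the rule as written sees no evaluable patients. One patient is 1/15 = 6.7 percentage points of Cohort B or C and 1/25 = 4 points of Cohort A.

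**4. Effect on the operating characteristics.** The documents give no rate for such events. Assume a fraction q of patients has a qualifying event before durvalumab, with q included in the true toxicity rate. Each lost patient still uses an enrolment place. Surgery rate 0.80. Pr(stop early) with these patients outside the toxicity rule:

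| N | True toxicity | q = 0 | q = 0.02 | q = 0.05 | q = 0.10 |
|---|---|---|---|---|---|
| 25 (Cohort A) | 0.30 | 0.27 | 0.23 | 0.18 | 0.10 |
| 25 (Cohort A) | 0.40 | 0.59 | 0.54 | 0.47 | 0.35 |
| 15 (Cohort B, if oleclumab is first) | 0.30 | 0.22 | 0.19 | 0.15 | 0.09 |
| 15 (Cohort B, if oleclumab is first) | 0.40 | 0.47 | 0.43 | 0.37 | 0.28 |

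These values are the same to two decimals whether or not the patient also drops out of the futility count. If the patient is instead entered as a non-event, the loss is larger: for Cohort A at 0.30, the values are 0.22, 0.15 and 0.08.

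**The case against.** - **The durvalumab dose is shorthand for Day 1.** Durvalumab is common to all cohorts, and 8.1.4 defines Day 1 as the first day of dosing. This is plausible as intent, but the phrase has no referent for a patient who never receives durvalumab. 13.3.3 (adjuvant toxicity) and 13.4 (summary report timing) use the first dose of immune-therapy instead.
- **11.1.1 makes every patient evaluable for toxicity from enrolment.** It does, but it does not widen the TOX window. At most it adds the patient to the denominator as a non-event, which the working shows is worse for the rule.
- **The events are rare.** This largely stands. 2.3.3 calls tremelimumab infusion effects rare, and the Cohort A grade 3/4 list in 2.6 contains no infusion reaction. Steroid-treatable grade 3 events that improve within 2 weeks are exempt anyway, so what is lost is chiefly grade 4 to 5 events or grade 3 events that do not improve. Values of q of 5% to 10% sit badly with this and mark an upper range. The 4-in-7 case lies right on the boundary.
- **Other safeguards exist.** Adverse events are collected from consent (7.4.1) and tabulated (13.4), and unexpected related life-threatening or fatal events go to the IND Office within 24 hours (7.5). These make the event visible but do not put it into the boundary.
- **Cohort A is nearly complete.** 13.2 expects about 25 patients by approval of the revision, so few interim decisions remain there. The closing verdict on the regimen still uses TOX.

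**Conclusion.** The gap is real in the text of the toxicity rule. In Cohort A, a qualifying related event between the start of tremelimumab and the start of durvalumab is not TOX. If durvalumab is never given, the patient does not become evaluable for toxicity. In Cohort B this depends on which of the conflicting order passages is followed. In Cohort C, 5.1 and 8.1.4 leave no such gap, but 5.1.2.3 also contains the reverse order.

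The practical effect is probably small: at q = 0.02 and true toxicity 0.30, Pr(stop early) falls by about 0.04 in Cohort A (0.266 to 0.228) and 0.03 at N = 15 (0.223 to 0.192). It rests on an assumed q and on the plan's independence assumption. The direction is clear: the printed operating characteristics overstate protection if any such events occur.

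A reader might infer three stronger things that the documents do not support:

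- That the patient also leaves the futility rule. 13.3 can be read as requiring both drugs or as naming the regimen, and the 13.3.1 table counts anyone whose surgery status is determined.
- That the surgery rate is therefore biased upward. A patient who reacts may still be resected, and dropping that patient would lower the rate; 2.6 reports that toxicity kept no patient from surgery.
- That partner-drug reactions are left out in every cohort. The order is uncontradicted only in Cohort A, and partner reactions that begin after durvalumab starts still count.

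This is a change that should be made, not a flaw that undermines the design.

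**What to change.** In the TOX definition, the TOX table heading (both 13.3.2) and the timing of checks in 13.3, replace the first-durvalumab-dose anchor with the start of the first infusion of any study drug. Let the 4-week period run from the same point. State in 13.3 that any patient who starts any study drug is evaluable for TOX and for surgery, which also settles the futility reading. Add a cross-reference so that 11.1.1 and 13.3.2 agree.

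Separately, reconcile the infusion-order passages: 5.1.2.2 against 5.1 and 8.1.4 for Cohort B, 5.1.2.3 against 5.1 and 8.1.4 for Cohort C, and the interval in 5.1.2.1 against 8.1.4 for Cohort A. Which order or interval applies is for the clinical team. The revised anchor works under any of them.

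The cost is a few words. No new data are needed, and the boundaries and printed operating characteristics stay as they are. Observed toxicity may look slightly less favourable.

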13.3.3 Interim Analyses for Toxicity Post Surgery Immune-therapy

Under the same model described for futility and toxicity above, toxicities on immune-therapy after surgery will be monitored assuming an a priori probability of toxicity following Beta(0.4,1.6) in the current treatment against a constant rate of 0.20. For trial monitoring and decisions about future trials, extreme toxicities (TOXpost) will be defined as any grade 3 or higher adverse event that is possibly, probably, or definitely related to any therapy received on this protocol and occur after surgery between the first dose of adjuvant immune-therapy and the final dose received (up to 12 weeks) with the following exception. Any grade 3 adverse event that is potentially treatable with steroids will only count as an extreme toxicity if it does not improve to grade 2 or better within 2 weeks. Grade 3 nausea or vomiting that responds to anti-emetics within 72 hours and asymptomatic grade 3 or 4 lipase or amylase elevations will not count as TOXpost. The trial will be terminated if $\text{Prob}(\text{TOXpost} > 0.20 \mid \text{data}) > 0.9$. Following this rule, the trial will be terminated according to the following table once the first 3 patients are evaluable.

If there are this many patients (or more) with TOXpost	2	3	4	5	6	7	8
Stop the cohort if there are this many (or fewer) patients who are evaluable (have TOXpost or completed 4 weeks after first adjuvant immune-therapy dose without TOXpost)	3	6	9	13	17	21	25*

* Only patients who successfully have surgery and begin treatment with immune-therapy will be included. The table goes to 25 patients as the maximum of possible patients.

Three patients in each cohort will be accrued first. If 2 of the 3 patients have TOXpost, stop this portion of the trial and the adjuvant treatment will be declared as too toxic for this population. Check continuously as described above for toxicity. The operating characteristics (OCs) for this stopping rule for are summarized in the following table assuming all 25 or 15 patients in each cohort receive surgery and start adjuvant immune-therapy. Since we do not expect all 25 or 15 patients to enter this portion of the study, the OCs are slightly over-estimated.

		Stop if $\text{Prob}(\text{TOXpost} > 0.20 \mid \text{data}) > 0.90$					
		Cohort A (N=25)			Cohorts B and C (N=15)		
True Toxicity Rate	Pr(stop early)	Mean Number of Patients	Median (25 th %ile, 75 th %ile)	Pr(stop early)	Mean Number of Patients	Median (25 th %ile, 75 th %ile)	
0.05	0.01	24.8	25 (25, 25)	0.01	14.9	15 (15, 15)	
0.10	0.04	24.2	25 (25, 25)	0.04	14.6	15 (15, 15)	
0.20	0.25	20.8	25 (24, 25)	0.20	13.1	15 (15, 15)	
0.30	0.62	15.2	16 (5, 25)	0.47	10.8	15 (5, 15)	
0.40	0.89	9.9	6 (3, 15)	0.73	8.3	6 (3, 15)	

